#### 5. STUDY INTERVENTIONS

#### 5.1 Interventions, Administration, and Duration

The intervention performed will either be a PFD or PFDD. It will be predetermined, based on cluster randomization, which procedure each center performs on their respective participants. A computer-generated randomization sequence will be generated independently by the study statistician. The surgery will occur in each respective center's operating room. With the exception of uniformly receiving the designated center intervention, all research participants will receive usual clinical care in accordance with institutional practice and judgment. Clinical care will include at a minimum an initial clinical evaluation by a participating pediatric neurosurgeon, surgical treatment (PFDD or PFD) and associated perioperative care, and routine post-operative care with prescribed follow-up clinical assessments at  $\leq 6$  weeks, 3-6 months, and 12 months (+/-2 months = 10-14 months) after surgery. Patients will be given the opportunity to re-consent into a study extension where any visits occurring within 5 years postoperatively will be documented, and the QOL questionnaires may be given annually. Research data will be collected at all stages by trained study research assistants/coordinators with strict oversight by site investigators using standard data collection forms. Neuro-imaging is a critical element of the trial, required both for enrollment and to monitor treatment efficacy. As such, MRI of the brain and cervical and thoracic spine are required prior to surgery. Pre-operative lumbar spine MRI will be left to the discretion of the surgeon. MRI of the cervical and thoracic spine are required 12 months (+/-2 months = 10 - 10 months)14 months) post-operatively. These are required for clinical care of CM+SM patients, regardless of participation in the study, and funding is not requested for these examinations. MRI of the lumbar spine, CT of the brain or cervical/thoracic/lumbar spine, "long cassette" or "scoliosis" Xrays, and/or X-rays of the cervical/thoracic/lumbar spine are not required but, will be reviewed if obtained. In the case where the patient returned outside the window for primary analyses, a secondary analysis will include those visits up to 24 months.

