    - External ventricular or lumbar drain placement
    - Shunt externalization or removal with or without external ventricular or lumbar drain placement
    - Shunt revision in the operating room
  - Chemical meningitis
    - Lumbar puncture
    - Steroids
  - Bacterial meningitis
    - Lumbar puncture
    - IV antibiotics
  - Cervical instability
    - External orthosis (e.g. cervical collar, halo vest)
    - Surgical fusion
    - Cerebellar ptosis
      - Cerebellopexy

Separate from these complications, other unexpected complications that are related to the surgery and other adverse events that occur that are not related to the surgery will be recorded for the < 6 month and 6-12 (+/- 2 months) month time intervals. Such events will be reported by site investigators. For inclusion of all followed patients in the case where the patient returned outside the planned study follow-up window, a secondary analysis will include those visits up to 24 months.

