#### Data Collection Procedures for Adverse Events

After enrollment, AEs, whether expected or unexpected, will be recorded according to the date of first occurrence, severity, duration, and any treatment prescribed. Any medical condition present at the time of enrollment, which remains unchanged or improved, will not be recorded as an adverse event on the Adverse Events Log. All study subjects will be monitored for adverse events from the time of enrollment until the time of discharge from the hospital and at each follow-up evaluation. Adverse events for subjects who withdraw from the study will be monitored and reported until the point of study withdrawal.

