Anticipated Outcome: PFD will have superior QOL and will show improvements in overall QOL over time (≤ 12 months post-operatively) compared to PFDD. In particular, both physical metrics (evaluated by pain frequency, pain severity and non-pain symptoms) and psychosocial metrics will improve at a higher rate and in a shorter period of time after PFD compared to PFDD. QOL will be assessed at the same time points using the Chiari Health Index Pediatrics (CHIP), and the Health Utilities-3 (HUI-3). For this aim, CHIP QOL (≤ 12 months post-operatively) will be used as the primary outcome, and HUI-3 and the domain sub-scores presented below will be assessed as the secondary outcomes. Additional, sensitivity analyses will be performed for the CHIP QOL based on the last reported CHIP QOL scores including up to 24 months post-operatively.

Corresponding Metrics for QOL:

Assumptions on dates and times were based on the following:

- Assuming 1 Month = 30 days
- From protocol, we wish to report CHIP assessments are at baseline, within 6 weeks of surgery, within 3-6 months of surgery and within 12 +/- 2 months of surgery.
- CHIP QOL was calculated via the method described in: https://thejns.org/pediatrics/view/journals/j-neurosurg-pediatr/17/1/article-p76.xml
- Only patients with complete entries were considered in the report.
- Domain sub-scores (sums of indicators) for each of the following domains of CHIP:
 - Pain Frequency
 - o Pain Severity
 - Non-Pain Symptoms
 - Psychosocial/Cognitive
- Overall QoL outcome (non-uniform weighted avg.) of the above 4 domains

2. STUDY DESIGN

This will be a cluster randomized control trial of 148 patients recruited from the 36 centers of the Park-Reeves Syringomyelia Research Consortium (PRSRC) as well as an additional 7 research centers. Randomization will occur at the center level with standardized surgical technique, and data will be recorded in the PRSRC prospective registry. In order to examine the main comparative effectiveness research (CER) question of surgical complications and potential harm to patients

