Second Chiari surgeries will be analyzed as 1) the proportion requiring a surgical revision and 2) the type of second surgery performed (same or cross-over). The 1-sided confidence interval for the difference in rates between the PFD and PFDD groups will be calculated and compared to the corresponding non-inferiority margins.

Specific Aim 3:

Hypothesis: With fewer surgical complications, PFD will be associated with superior QOL compared with PFDD.

Anticipated Outcome: PFD will have superior QOL and will show improvements in overall QOL over time (≤ 12 months post-operatively (± 2 months)) compared to PFDD. In particular, both physical metrics (evaluated by pain frequency, pain severity and non-pain symptoms) and psychosocial metrics will improve at a higher rate and in a shorter period of time after PFD compared to PFDD.

Secondary outcomes include Treatment Efficacy variables and Quality of Life variables. Continuous variables measured at 3 time points over the 12-month follow-up will be analyzed using longitudinal analysis with linear mixed models including the random cluster effect. Binomial and ordinal data will be analyzed using Mixed Model methods accounting for cluster. In addition, sensitivity analyses will be conducted where the missing data points will be imputed based on the last observation carried forward.

It should be noted that for Aim 3, primary analyses will be based on the QoL exam performed at 10 to 14-month window. A sensitivity analyses will also be performed based on the last QoL exam available at any time \geq 3 months after surgery. Analyses based on the mixed effect model will also be performed where both cluster effect and error terms will be random.

Missing data: Based on PRSRC data and early data from this trial, loss to follow-up rate is expected to be low (<2%). To prevent missing data, we will meet with patients at 1 month, 3-6 months and at 12+/-2 months after the procedure. Every effort, including phone call reminders to patients, will be made to decrease loss to follow-up. Loss to follow-up, missing data, and the reasons leading to loss of follow-up or data will be recorded. In case of missing data, we will impute missing data using different methods. Because of the repeated measures nature of the data, the 'last observation

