Sub-analysis by Syrinx size (3-6 mm, 7-9 mm): A planned subgroup analysis for each of the 3 to 6 mm and 7 to 9 mm syrinx diameters will be performed for each of the 3 aims. The test of interaction will be used to assess if the treatment effect is homogeneous within each of the syrinx size subgroups (3- 6 mm vs 7-9 mm). If the test of interaction indicates heterogeneity, using the whole 3 to 9 mm syrinx diameter range, analyses will be performed, to identify, if any, a cut-off point to propose using one surgical method over the other. For example, whether the PFD is associated with greatly fewer surgical complications when the syrinx diameter is less than 5mm, but surgical complication rates are similar for PFD and PFDD when the syrinx diameter is \geq 6 mm will be examined.

Secondary Analysis

The aims will be evaluated using the overall population who were followed from 6 months to 24 months after enrollment. Analysis will be performed to compare the per Treatment groups for time to last follow-up in order to determine if there is differential follow-up times between groups. Analysis of Aims 2 and 3 will be similar to the primary analysis with adjustment for time to last follow-up as a covariate.

Aim 3 includes some questions that may not be applicable for younger children. For example, keeping up with schoolwork or difficulty with math. Therefore, for this ,a subgroup analysis for

those children age >5 years will also be performed. Additional analysis will include subdomain comparisons of: Pain symptoms Headache Back pain Non-pain symptoms Difficulty raising arms Difficulty walking Frequently lose balance Psychosocial Tired Easily frustrated Trouble sleeping Difficulty concentrating Difficulty paying attention in class Forgetful Difficulty with reading Difficulty with math Difficulty learning new things Difficulty keeping up with schoolwork. Covariates in this analysis will include medical history (Autism, ADHD, Known Psych Disease),

pathology (known Craniofacial Anomalies, Known Skull Malformation, Known Hydrocephalus, Known Spine Column Disorder) and Syrinx (Syrinx Level Known, Syrinx AP Diameter).

Exploratory Analysis

Additional exploratory subgroup analyses will be performed for Aims 2 and 3. These analyses will include age (<5,5-12,13-18), CM status (5-12,>12 mm), and preoperative hydrocephalus or neuromuscular disease. These analyses will examine if there is differential response between the groups.

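### The SAP's 6-to-24-month secondary analysis, read literally, drops patients who die, withdraw or are lost before 6 months, along with their Aim 1 events, and counts from enrollment although endpoints count from surgery

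*SAP*

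**What the plan says.** SAP 7.5, under Secondary Analysis, defines one population for all three aims: "The aims will be evaluated using the overall population who were followed from 6 months to 24 months after enrollment". It then plans to "compare the per Treatment groups for time to last follow-up in order to determine if there is differential follow-up times between groups", and adjusts Aims 2 and 3 for time to last follow-up. No adjustment is stated for Aim 1, and the paragraph does not say which visit supplies the outcome.

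The protocol describes its 24-month analysis in section 5.1, under SAFETY ASSESSMENTS, in 9.1 and in 9.5. Each time, it brings in visits up to 24 months for patients who came back outside the planned window. The safety section gives the purpose: "For inclusion of all followed patients in the case where the patient returned outside the planned study follow-up window". None of these places sets a 6-month minimum.

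The SAP has two other analyses that use late scores, both for Aim 3 and both timed from surgery. In section 1.2, "sensitivity analyses will be performed for the CHIP QOL based on the last reported CHIP QOL scores including up to 24 months post-operatively". In section 7.5, "A sensitivity analyses will also be performed based on the last QoL exam available at any time" from 3 months after surgery onward. The Aim 3 primary result is fixed elsewhere in 7.5: "primary analyses will be based on the QoL exam performed at 10 to 14-month window".

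**The concern.** Aim 1 measures harm, and much of that harm is expected early. The anticipated CSF-related complications fall within 6 months of surgery, and the outcome list in SAP 7.5.1 includes intra-operative death. A rule requiring 6 months of follow-up therefore selects on something the outcome itself can cause. A child who dies at operation, or who has a complication and then withdraws, leaves the analysis and takes the event along. The data need not be lost: "Adverse events for subjects who withdraw from the study will be monitored and reported until the point of study withdrawal".

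The clock is a second problem. Protocol 6.2.2 has consent signed before surgery, so time since enrollment exceeds time since surgery by an interval that differs between patients.

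At stake is the value of a supporting analysis. The protocol meant it to be more inclusive than the primary analysis; as the SAP words it, it can be less inclusive at the early end. Agreement with the primary result would then be weaker reassurance than it appears.

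**Working it through.** **1. The rules side by side**

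| Analysis | Minimum follow-up | Clock | Upper limit | Visit used |
|---|---|---|---|---|
| Protocol 24-month analysis (5.1, safety section, 9.1, 9.5) | none stated | post-operative follow-up window | 24 months | visits outside the window |
| SAP Secondary Analysis (7.5), all aims | 6 months | enrollment | 24 months | not stated |
| SAP CHIP sensitivity analysis (1.2) | none stated | surgery | 24 months | last score |
| SAP QoL sensitivity analysis (7.5) | 3 months | surgery | none stated | last exam |

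The 6-month floor and the enrollment clock appear only in the second row. The explicit last-score rules appear only in the third and fourth.

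**2. The clock.** If surgery follows enrollment by g months, 6 to 24 months after enrollment is (6 − g) to (24 − g) months after surgery. The documents do not give g.

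**3. How many patients.** First the plan's own figure (SAP 7.2): 145 / (1 − 0.02) = 147.96, rounded up to 148, which agrees. Then:
- planned loss of 2%: 0.02 × 148 = 3.0 patients;
- observed loss of 1 in 100: 0.01 × 148 = 1.5 patients.

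Both rates are for loss at any time, so they are upper bounds on loss before 6 months.

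**4. Effect on Aim 1.** With 74 per group and the planned rates, expected events are 0.178 × 74 = 13.2 (PFDD) and 0.027 × 74 = 2.0 (PFD). Taking 13 and 2, and removing k PFDD patients who had an early event, the difference is (13 − k)/(74 − k) − 2/74:

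| k | PFDD rate | Difference from 2.7% |
|---|---|---|
| 0 | 13/74 = 17.6% | 14.9 points |
| 1 | 12/73 = 16.4% | 13.7 points |
| 2 | 11/72 = 15.3% | 12.6 points |
| 3 | 10/71 = 14.1% | 11.4 points |

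Removing one PFD event instead gives 13/74 − 1/73 = 16.2 points. The distortion can go either way.

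**5. If loss is unrelated to outcome (assumption).** With 1.5 patients lost per arm, expected dropped events are 1.5 × 0.178 = 0.27 (PFDD) and 1.5 × 0.027 = 0.04 (PFD), which is negligible.

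**6. Power.** SAP 7.2 states 82% for Aim 3 with 68 per group, a difference of 0.20 − 0.12 = 0.08 and SD 0.16. The normal approximation gives 0.08 / (0.16 × √(2/68)) = 2.92, and 2.92 − 1.96 = 0.96, so about 83%, close to the stated figure. Excluding 2% leaves 74 × 0.98 = 72.5 per group. Divided by the plan's design effect of 1.06 this is 68.4, again about 83%. The issue is selection, not power.

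**7. Why the visit rule matters.** Suppose the last visit is used, and a share f of one arm has its 12-month CHIP score replaced by a later score differing by c. That arm's mean moves by f × c: 0.10 × 0.08 = 0.008, or 0.50 × 0.08 = 0.04, against a planned difference of 0.08. Both f and c are assumptions; the documents give neither.

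**The case against.** The strongest reply is that little is affected. The Aim 1 primary outcome stays at 12 (±2) months from initial surgery, and the Aim 3 primary result stays on the 10-to-14-month exam. Expected loss is below 2%, and the SAP already plans complete-case, last-observation and Buck's-method comparisons. The sentence may also have been meant to describe the range of visits, not to exclude anyone. All of this limits the size of the point. It does not settle what the sentence tells the analyst to do, and the missing-data comparisons do not restore patients whom the population definition removes.

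A reader might infer more than the documents support:

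- *That 12-month results are overwritten.* They are not. Later scores can displace an in-window score only inside supporting analyses, and asking whether a last-score analysis agrees with the primary one is a legitimate sensitivity question.
- *That late values come only from self-selected extension patients.* Protocol 5.1 does say "Patients will be given the opportunity to re-consent into a study extension where any visits occurring within 5 years postoperatively will be documented", so selection is plausible. But the same section separately foresees patients who simply return late, without mentioning re-consent. The schedule in 6.1 marks CHIP and HUI-3 as required after 14 months, although clinical items and imaging are optional. No re-consent share is given, so no count of replaced scores can be derived.
- *That the PFD complication rate would be halved.* Losing one of two expected PFD events does take 2/74 = 2.7% to 1/73 = 1.4%. That is a chosen worst case, worth about 1.3 points on the difference.
- *That adjusting for time to last follow-up is an error.* Where assessments span 6 to 24 months, adjusting for timing is defensible, and the SAP tests whether follow-up differs between groups without asserting that it does. What stands is narrower: follow-up time arises after surgery and could be affected by treatment, so one adjusted result is not enough on its own.

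**Conclusion.** The point holds for the population and the clock of the SAP's Secondary Analysis. Taken literally, the wording excludes early deaths, withdrawals and losses from all aims, removes recorded Aim 1 events, and times follow-up from a different origin than the endpoints. It departs from a protocol analysis whose stated purpose was to include all followed patients, so the two documents must be reconciled.

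The size is modest: a non-primary analysis and at most about 3 of 148 patients. The shift of 1.1 to 3.5 points in the Aim 1 difference (14.9 − 13.7 is 1.1 before rounding; 14.9 − 11.4 = 3.5) assumes that those lost are PFDD patients with early events. If loss is unrelated to outcome, the effect is negligible. The documents do not show which case applies, and the correction costs almost nothing, so it is worth making before the analysis is run.

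**What to change.** Rewrite the Secondary Analysis paragraph in SAP 7.5 along these lines:

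- **Population and clock:** all enrolled, operated patients, with time counted from the initial surgery.
- **Aim 1:** every recorded event counts, whatever the patient's later follow-up.
- **Aims 2 and 3:** use the 10-to-14-month assessment when there is one. Only when it is absent, use the out-of-window visit closest to 12 months, up to 24 months. This follows the protocol's purpose, and SAP 1.2 already applies a closest-to-12-months rule for Aim 2 when there are several visits.
- **Reporting:** give follow-up time by arm and the number of values taken after 14 months.
- **Covariate:** show Aims 2 and 3 both with and without adjustment for time to last follow-up.

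The two Aim 3 last-score analyses can stay as they are, labelled as separate sensitivity analyses.

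The cost is SAP wording and one extra unadjusted set of results; no new data are needed. Some late-visit data would go unused in this analysis and can be described separately. With loss this low, the result may lie close to the primary analysis.

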7.5.1 Metrics

Primary Outcome: measured as a binary (yes/no) variable. The presence of any of the following items will be considered as a poor outcome (harm to patients):

• Intra-operative Complication

- Vascular injury resulting in dissection or stroke
- Intracranial hemorrhage requiring return to surgery for evacuation
- Neurological injury (new cranial nerve deficit, weakness, sensory loss, bowel or bladder dysfunction)
- Death

• Complication ≤ 12 (+/- 2 months) months after initial PFDD or PFD

- Pseudomeningocele: extradural and/or subcutaneous fluid collection resulting in discomfort or pain, limitation of movement, or CSF leak. Radiological evidence of fluid collection alone is not sufficient for diagnosis of pseudomeningocele.
- CSF leak
- Hydrocephalus: requires external drainage, shunting, or endoscopic 3rd ventriculostomy
- Infection: clinical diagnosis that may include fever, wound drainage, dehiscence, or elevated laboratory parameters in association with antibiotic treatment ± surgical debridement.
- Chemical (or aseptic) meningitis: clinical diagnosis prompting medical treatment (e.g. steroids); lumbar puncture and analysis of CSF cell profile not required but will be tracked if available.
- Cervical instability
- Need for surgical procedures for complication management ≤12 (+/- 2 months) months after initial PFDD or PFD
 - External drainage for the following:
 - > Hydrocephalus
 - ➢ CSF leak
 - Pseudomeningocele
 - ➢ Infection
 - Shunt malfunction/infection
 - Simple over-sewing of wound for CSF leak
 - Surgical revision in operating room for the following:
 - ➢ CSF leak
 - ➢ Infection
 - > Pseudomeningocele
 - Lumbar puncture and steroids for the following:
 - Chemical meningitis
 - True meningitis
 - Implantation of ventriculo-peritoneal or other permanent shunt or endoscopic 3rd ventriculostomy for hydrocephalus.
 - Cervical collar and/or fusion for cervical instability

Secondary Outcomes:

- Treatment Efficacy, measured ≤6 weeks, 3-6 months, and 12 (+/- 2 months) months after surgery:
 - Status of clinical symptoms
 - Status of neurological findings
 - Syrinx diameter (in mm)
 - Spinal alignment (coronal and sagittal Cobb angles)
 - Need for revision of PFDD or PFD
- Quality of life, measured ≤6 weeks, 3-6 months, and 12 (+/- 2 months) months after surgery:

- Chiari Health Index in Pediatrics (CHIP)
- HUI-3.

7.5.2 Protocol Deviations

Protocol deviations will be reported to the local IRB per the respective institution's guidelines.

7.5.3 Monitoring

The DCC will monitor data quality primarily through the use of remote monitoring activities. Remote monitoring involves detailed review of the data entered by the Clinical Center and consultations with the Clinical Center investigator and/or research assistant/coordinator to review safety and data quality. This may require uploading deidentified copies of specific parts of the medical record, patient study file, regulatory documentation, or other source documents to the DCC staff who will review those materials against the data recorded in the electronic data capture system. This helps assure protocol compliance and accurate data collection. The DCC may conduct more remote monitoring activities early in the trial to assure protocol compliance and identify any training issues that may exist. Safety of subjects will be monitored and ensured in accordance with the DSMB plan. The medical record and study files (including informed consent, permission, and assent documents) must be made available to authorized representatives of the DCC, upon request, for source verification of study documentation. In addition, medical information and data generated by this study must be available for inspection upon request by representatives of the IRB for each study site.
